9.5 Database closure

Prior to database closure, all tasks or criteria defined in the data management plan must be completed and documented. The study database must be locked before breaking of the blind and before generation of any results. The database lock will be approved by relevant study personnel and all edit accesses will be removed. The study database can only be unlocked in case critical errors, affecting the main conclusions of the study, are discovered.

9.6 Record retention

The investigator should maintain a record of the location(s) of investigator's essential documents as defined in the ICH GCP Guideline (1) including source documents and should have control of and continuous access to all essential documents and records generated by the investigator/institution before, during, and after the study.

All documents and data relating to the study will be kept securely by the investigator in a secure file and/or electronically. The storage system used during the study and for archiving (irrespective of the type of media used) should provide for document identification, version history, search and retrieval. The data will be available for evaluation and/or audits from Health Authorities, Sobi or Sobi's representatives.

When a copy is used to replace an original document (e.g. source documents, EDC), the copy should fulfill the requirements for certified copy as defined in ICH GCP Guideline (1).

The records should be retained by the Investigator as specified in the Clinical Trial Agreement and in accordance with local regulations.

10 End of study

The end of this study is defined as the date of last subject out, i.e., the last subject's last visit.

11 Sponsor's discontinuation criteria

Sobi reserves the right to discontinue the study prior to inclusion of the intended number of subjects but intends only to exercise this right for valid scientific or administrative reasons. After such a decision, the investigator must contact all participating subjects within 10 days. All study materials must be collected and all the CRFs completed to the greatest extent possible.

12 Dissemination and publication of results

Sobi will register the study by posting study information and post study results regardless of outcome on a publicly accessible website in accordance with applicable laws and regulations, e.g., on www.clinicaltrials.gov.

Sobi is committed to publishing study results in a complete, accurate, balanced, transparent and timely manner. Sobi follows the principles of the International Committee of Medical Journal Editors (ICMJE) recommendations for the conduct, reporting, editing, and publication of scholarly work in medical journals including criteria for authorship (27).

## 1 Abbreviations and definition of terms

---

ADA	Anti-drug antibodies
ADR	Adverse drug reaction
AE	Adverse event
BMI	Body mass index
CSR	Clinical study report
CRO	Contract research organization
CXCL9	CXC chemokine ligand 9
DBL	Database lock
FSI	First subject in
IFN $\gamma$	Interferon-gamma
IMP	Investigational medicinal product
i.v.	Intravenous
LLOQ	Lower limit of quantification
mITT	Modified intention-to-treat population
nAbs	Neutralizing antibodies
PCR	Polymerase chain reaction
PD	Pharmacodynamics
PT	Preferred Term
PK	Pharmacokinetics
SADR	Serious adverse drug reaction
SAE	Serious adverse event
SAP	Statistical analysis plan
SARS-CoV-19	Severe acute respiratory syndrome coronavirus 19
sIL2R	Soluble interleukin-2 receptor
Sobi	Swedish Orphan Biovitrum

---

SOC	System Organ Class
TEAE	Treatment-emergent adverse event

---

## 2 Introduction

This Statistical Analysis Plan (SAP) describes the planned analysis and reporting for the Sobi protocol Sobi.emapalumab-102 (A randomized, double-blinded, placebo-controlled, single center, phase I study to evaluate pharmacokinetics, pharmacodynamics and safety of emapalumab after a single intravenous dose in Japanese healthy volunteers.).

This phase I study is being completed to assess the pharmacokinetics, pharmacodynamics and safety of emapalumab in healthy Japanese subjects following a single i.v. dose of emapalumab.

The purpose of this SAP is to outline the planned analyses to be completed to support the Clinical Study Report (CSR) for protocol Sobi.emapalumab-102. The planned analyses identified in this SAP will be included in regulatory submissions and/or future manuscripts. Also, exploratory analyses not necessarily identified in this SAP may be performed to support the clinical development program. Any post-hoc, or unplanned, analyses not identified in this SAP will be clearly identified in the respective CSR.

The structure and content of this SAP provides sufficient detail to meet the requirements identified by the FDA and International Council on Harmonisation of Technical Requirements for Registration of Pharmaceuticals for Human Use (ICH): Guidance on Statistical Principles in Clinical Trials. All work planned and reported for this SAP will follow internationally accepted guidelines, published by the American Statistical Association and the Royal Statistical Society, for statistical practice.

## 3 Study objectives and endpoints

### 3.1 Primary objective

The primary objective is to evaluate the pharmacokinetics (PK) and pharmacodynamics (PD) of emapalumab in healthy Japanese subjects following a single intravenous (i.v) dose of emapalumab.

### 3.2 Secondary objectives

The secondary objectives are as follows:

- To assess safety in healthy Japanese subjects following a single intravenous dose of emapalumab
- To investigate immunogenicity of emapalumab

### **3.3 Study endpoints**

#### **3.3.1 Primary endpoints**

The primary endpoints are as follows:

- PK parameters:  $C_{max}$ ,  $t_{max}$ , CEOI,  $AUC_{last}$ ,  $AUC_{inf}$ , % $AUC_{extr}$ ,  $\lambda_z$ ,  $t_{1/2}$ , CL,  $V_{ss}$ ,  $MRT_{last}$  and  $MRT_{inf}$ .
- PD biomarkers:
  - Pre-dose circulating IFN $\gamma$  concentration
  - Total IFN $\gamma$  concentrations
  - CXCL9 concentration
  - sIL2R concentration

#### **3.3.2 Secondary endpoints supporting the secondary objectives**

The study has the following secondary endpoints:

- Adverse Events
- Laboratory parameters
- The presence of anti-drug antibodies (ADAs) and neutralizing antibodies (nAbs)

## **4 Study methods**

### **4.1 Overall study design and plan**

[figure not shown]
This is a randomized, placebo-controlled and double-blinded study to evaluate the PK, PD and safety of a single i.v. dose (1 mg/kg) of emapalumab in adult healthy Japanese subjects, performed in Japan. 8 subjects will be randomized to receive either emapalumab or matching placebo in a 3:1 ratio (emapalumab: placebo). The investigator, study subjects and sponsor will be blinded to treatment allocation (placebo and active) to avoid reporting, assessment and allocation biases. It is considered sufficient with 6 subjects randomized to emapalumab, considering the inter-subject variability in the PK results in the NI-0501-03 study.

Figure 1 shows the study design.

Study subjects will be screened within 21 days prior to administration of investigational medicinal products (IMP). An additional visit will take place within 96 hours prior to IMP infusion for collection of a PCR test for SARS-CoV-2. Eligible subjects will be admitted to the clinical unit the day before drug administration (Study Day -1). On Day 1 of the admission

period subjects will receive a single dose of emapalumab (1 mg/kg) or placebo administered as a 1-hour infusion. Subjects will be discharged from the unit on Day 8. PK samples will be collected up to Week 14 in order to measure the emapalumab serum levels during at least 3 times the terminal half-life (a total of approximately 3 months). All subjects will be followed-up on regular visits for a minimum of 14 weeks after a single infusion of emapalumab. In addition, any subject with ongoing SAEs at study completion will be followed-up until resolution of the event or until the outcome is known and stable.

**Figure 1** **Study Design Sobi.emapalumab-102**

Abbreviations: IMP, investigational medicinal product W, study week.

## 4.2 Selection of study population

Refer to protocol section 6.5 Selection of study population for inclusion and exclusion criteria

## 4.3 Method of treatment assignment and randomization

The different treatment groups are:

Arm A: Emapalumab

Arm B: Placebo (saline)

One randomization list will be prepared by the CRO. The ratio between the treatment groups is 3:1, i.e., 6 subjects will be randomized to emapalumab, and 2 subjects will be randomized to placebo/saline.

Until the time of unblinding for final data analysis, the randomization list is kept strictly confidential, and accessible only to authorized persons.

Full randomization information will be made available for data analysis only after database closure in accordance with Sobi SOPs.

## 5 Sequence of planned analysis

### 5.1 Interim analyses

There is no planned Interim Analysis for this study.

### 5.2 Analyses and reporting

All final, planned, analyses identified in the protocol and in this SAP will be performed only after the last subject has completed the study. The SAP will be finalized before FSI. If any revision is made, the SAP will be finalized, locked and signed prior to DBL.

## 6 Sample size determination

This is a phase I study to evaluate the PK and PD of emapalumab in healthy Japanese subjects following single dose administration of emapalumab. No formal sample size calculation was made but the sample size was chosen based on previous experience in phase I studies. Also, 6 subjects receiving emapalumab are considered sufficient, considering the inter-subject variability in the PK results in the NI-0501-03 study, and 2 subjects receiving placebo is considered a reasonable number. In study NI-0501-03 the CV for inter-subject variability was within 30 % for PK parameters such as  $C_{max}$  and AUC % based on 4 subjects at a dose level of 1 mg/kg emapalumab.

## 7 Analysis populations

The analysis sets that will be used in the statistical analyses are described in Section 7.1 (mITT), Section 7.2 (PK/PD population) and Section 7.3 (Safety Analysis population).

### 7.1 Modified intention-to-treat population (mITT)

The mITT will comprise all randomized subjects who received an infusion of IMP and have at least one blood draw to determine PK and PD. This analysis population will not be used in any statistical analyses.

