8.2 Definition of study populations

All analyses will be conducted on the modified intention-to-treat (mITT) population which will comprise all randomized subjects who received an infusion of IMP and have at least one blood draw to determine PK and PD.

The Safety population will comprise of all patients who received an infusion of IMP.

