### 7.2 PK/PD Analysis population

A PK/PD population will be used for analyzing the primary endpoints. This population comprises all randomized subjects who received an infusion of Emapalumab, without any protocol deviations affecting PK/PD evaluation. All analyses using the PK/PD population will group subjects according to treatment actually received.

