## **9.3 Analysis Dataset**

Population: Randomized Subjects

Group: Emapalumab, Placebo

Contents:

- Calculate the number and percentages of subjects by groups in the following population:

- Randomized Subjects
- Safety Analysis population (Qualified/Unqualified)
- PK/PD population (Qualified/Unqualified)
- Calculate the number of unqualified subjects by reasons in PK/PD and Safety Analysis population.

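### Protocol 8.2 puts all analyses on the mITT set; the SAP uses that set in none and summarizes the primary endpoints on an emapalumab-only set, so placebo drops out of the primary PD summaries

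*SAP*

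**What the plan says.** - **Protocol 8.2** names one set for everything: "All analyses will be conducted on the modified intention-to-treat (mITT) population which will comprise all randomized subjects who received an infusion of IMP". The definition goes on to require at least one PK/PD blood draw. It covers both arms and has no exclusion for deviations. The same section also defines a Safety population but assigns no analysis to it.
- **SAP 7.1** repeats the mITT definition and then adds: "This analysis population will not be used in any statistical analyses". The opening of SAP 7 nevertheless lists mITT among the sets to be used.
- **SAP 7.2** sets the replacement: "A PK/PD population will be used for analyzing the primary endpoints". Its membership is: "This population comprises all randomized subjects who received an infusion of Emapalumab, without any protocol deviations affecting PK/PD evaluation". Subjects are grouped by treatment actually received. The protocol defines no such set.
- **SAP 14.1**, below the PK parameter table, adds a second exclusion rule for subjects whose data do not permit an accurate PK assessment. Incomplete dosing and insufficient concentration data are among its examples.
- **SAP 9.3** asks: "Calculate the number of unqualified subjects by reasons in PK/PD and Safety Analysis population". mITT is not counted there.

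**The concern.** The protocol and the SAP give incompatible instructions on who enters the primary analysis, and no other section says which prevails. Protocol 8.3.1 asks the SAP to describe the analyses in detail. It does not say that the SAP may replace the analysis set, and the SAP does not flag the replacement as a departure from the protocol.

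Two things are at stake. First, PD biomarkers are primary endpoints, and the placebo subjects are the only concurrent reference for them. Protocol 4.1.2.3 itself describes total IFNγ in the earlier healthy-volunteer study by contrasting flat placebo levels with rising levels on emapalumab. Second, with only six subjects planned on emapalumab, losing any one of them to an exclusion is felt in every PK summary. Neither SAP 7.2 nor SAP 9.2 lists which deviations count as affecting PK or PD, and neither document says when that judgement must be made.

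**Working it through.** **Step 1. Planned numbers.** Protocol 6.1 and 6.6 give 8 subjects at 3:1, so 8 × 3/4 = 6 on emapalumab and 8 × 1/4 = 2 on placebo. This agrees with the stated split.

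**Step 2. The sets side by side.**

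| Set | Rule | Emapalumab | Placebo |
|---|---|---|---|
| mITT (Protocol 8.2, SAP 7.1) | randomized, infused with either product, at least one PK/PD draw | up to 6 | up to 2 |
| PK/PD (SAP 7.2) | randomized, infused with emapalumab, no deviation affecting PK/PD | at most 6 | 0 |
| Safety (SAP 7.3) | infused with either product | up to 6 | up to 2 |

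The zero in the placebo column follows from the definition: membership requires an emapalumab infusion, and grouping is by treatment received.

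**Step 3. Where the PK/PD set is used.**

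- SAP 14.2.1 to 14.2.3 (PD table and figures): PK/PD population, emapalumab group only. Both placebo subjects are absent from the primary PD summaries.
- SAP 10.1 (demographics) and SAP 15.4.1 (ADA and nAbs): PK/PD population, with emapalumab and placebo groups requested. The placebo group is empty in both.
- SAP 14.1.1 to 14.1.4 (PK): PK/PD population, emapalumab only. Leaving placebo out is natural here, because these subjects have no emapalumab exposure.

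**Step 4. Precision if one emapalumab subject is excluded.** Inputs: CV within 30% (Protocol 8.1, SAP 6), taken at its ceiling. SAP 8.3.1 plans a 95% interval for the geometric mean but gives no formula, so I assume a t interval on the log scale.

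- Log-SD = sqrt(ln(1 + 0.30²)) = sqrt(ln 1.09) = 0.2936.
- n = 6: half-width 2.571 × 0.2936 / sqrt(6) = 0.308, giving 0.735 to 1.361 times the estimate.
- n = 5: half-width 2.776 × 0.2936 / sqrt(5) = 0.365, giving 0.695 to 1.440.
- At an assumed CV of 20%: 0.812 to 1.231 (n = 6) and 0.782 to 1.279 (n = 5).

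**Step 5. Shift in the point estimate.** If the excluded subject lies z log-SDs from the mean of the other five, the mean log of all six differs from that of the five by z × SD / 6. The geometric means therefore differ by a factor exp(0.2936 z / 6), which is 1.05 for z = 1 and 1.10 for z = 2. At a CV of 20% (log-SD 0.198) the factors are 1.03 and 1.07.

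**Step 6. How likely an exclusion is.** The documents give no rate. If each of the six independently had an assumed 5%, 10% or 20% chance, the chance of at least one exclusion is 1 - 0.95⁶ = 26%, 1 - 0.90⁶ = 47% or 1 - 0.80⁶ = 74%.

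**The case against.** The strongest reply is that a PK set restricted to drug recipients is sensible. Applied literally, the protocol's mITT would put placebo subjects into emapalumab PK parameter summaries. Protocol 8.2 is also loosely drafted, since it claims all analyses for mITT and then defines a Safety population. There is no test, margin or decision rule to overturn. Protocol 8.3.1 has all data listed, SAP 9.3 tabulates unqualified subjects by reason, and SAP 16 lists concentrations, PK parameters and biomarkers. Among six subjects an exclusion would be seen. All of this stands. It lowers the severity but does not say which set governs, and it does not restore placebo to the PD summaries.

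Three stronger readings are tempting, and the documents do not support them.

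- *The switch was concealed because SAP 18 is silent on it.* That history logs changes between SAP versions 1.0 and 2.0, not departures from the protocol, and SAP 7.1 states openly that mITT is unused. Its absence from the SAP 9.3 counts follows from that and is not a second defect.
- *The set will be chosen with treatment and results in view.* Any drug-recipient PK set, including the one proposed below, can be completed only once codes are released. Protocol 9.5 requires database lock before the blind is broken and before results are generated. What remains is narrower: no date is set for judging which deviations matter.
- *Every emapalumab subject with a deviation is dropped.* SAP 7.2 is limited to deviations affecting the PK/PD evaluation.

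**Conclusion.** The conflict over the primary analysis set is real and unresolved. It should be fixed, but it does not threaten the validity of the study.

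The loss of both placebo subjects from the primary PD summaries, and the empty placebo groups in two SAP tables, follow from the definitions and need no assumption beyond the planned 6:2 split being delivered.

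The effect on PK is conditional. It needs an actual exclusion under SAP 7.2 or SAP 14.1. At the 30% ceiling, one exclusion changes the 95% interval from 0.73-1.36 to 0.69-1.44 times the geometric mean, an upper-to-lower ratio of 2.07 instead of 1.85. A reader might take the 5% to 10% shift in Step 5 as the expected bias. It is only what would follow if the excluded subject happened to lie 1 to 2 SDs from the rest, and it falls well inside the six-subject interval.

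**What to change.** Align Protocol 8.2 with SAP 7.1 to 7.3, including the opening of SAP 7, so that each endpoint has one named set.

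1. **PD and ADA/nAbs:** summarize on mITT or another both-arm set, by treatment received, with placebo shown (SAP 14.2 and 15.4.1). Present the demographics in SAP 10.1 on sets in which the requested groups can exist.
2. **PK:** summarize on all emapalumab recipients with at least one quantifiable post-dose sample. This is narrower than the protocol's mITT, so give it its own name and define it in both documents. Whenever anyone is excluded under SAP 7.2 or SAP 14.1, show the summary after exclusions alongside.
3. **Timing:** for all eight subjects, classify which deviations affect PK or PD before unblinding and before concentrations are released.
4. **Reporting:** count each set in SAP 9.3, and record the departure from Protocol 8.2.

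Cost: protocol and SAP wording and a few extra summary tables. No new data are needed.

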### 7.2 PK/PD Analysis population

A PK/PD population will be used for analyzing the primary endpoints. This population comprises all randomized subjects who received an infusion of Emapalumab, without any protocol deviations affecting PK/PD evaluation. All analyses using the PK/PD population will group subjects according to treatment actually received.

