### 8.3.2 Percentages

Percentage is calculated using the following formula (unless otherwise indicated):

$$\text{Percentage (\%)} = \frac{\text{the number of applicable subjects}}{\text{the number of subjects within the treatment group for the population of interest}} \times 100$$

Percentages will be suppressed when the count is zero, however the category will still be displayed.

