## 10 Demographics and baseline characteristics

### 10.1 Demographics and Other Baseline Characteristics

Population: Safety Analysis population, PK/PD Analysis population

Group: Emapalumab, Placebo

Contents:

- For categorical data and ordinal data, calculate the number of subjects and percentages.
- For continuous data, calculate the descriptive statistics.

Definitions:

- BMI  
BMI at screening will be calculated using the following formula:

$$\text{BMI} = \frac{\text{Weight [kg]}}{(\text{Height [m]})^2}$$

- Unknown and Missing values  
If unknown or missing values are observed, add “Unknown” category and only calculate the number of subjects. Remove “Unknown” category from the denominator for percentages.
- Race is only displayed in the listing.

[Background Factors]

Classification [Unit]	Category
Age [Year]	<30, 30≤ <40, 40≤
	Descriptive statistics
Sex	Male, Female
Height [cm]	Descriptive statistics
Weight [kg]	Descriptive statistics
BMI [kg/m  ]	Descriptive statistics

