### 15.4.1 The presence of ADAs and nAbs

Population: PK/PD population

Group: Emapalumab, Placebo

Contents:

- Calculate the number of subjects with positive with ADA/nAbs in Table 8 in 15.4 Anti-drug antibodies at baseline and at study completion or withdrawal (defined in Table 3 in 8.4.3 Visit Windows) by groups.
- Denominator to calculate the percentages: The number of subjects from the population in each group.

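### SAP 15.4.1 asks for a placebo ADA/nAb column from an emapalumab-only population (denominator 0 instead of 2); separately, SAP 14.2 leaves placebo out of every PD table and figure and plans no PD change from baseline

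*SAP*

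**What the plan says.** SAP 7.2 defines the PK/PD population for the primary endpoints: "This population comprises all randomized subjects who received an infusion of Emapalumab, without any protocol deviations affecting PK/PD evaluation". It adds: "All analyses using the PK/PD population will group subjects according to treatment actually received".

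SAP 15.4.1, the ADA/nAb table, specifies "Population: PK/PD population" and "Group: Emapalumab, Placebo", with the number of subjects in each group as denominator. It belongs to Section 15 (safety analyses), and SAP 7.3 assigns safety analyses to the Safety Analysis population, which is everyone who received IMP. SAP 10.1 (demographics) asks for both groups under "Population: Safety Analysis population, PK/PD Analysis population".

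The three PD outputs (SAP 14.2.1 to 14.2.3) use the PK/PD population, and their group lines name emapalumab only. None includes change from baseline. SAP Section 7 introduces its three sets, the mITT among them, as those that will be used, but SAP 7.1 says of the mITT: "This analysis population will not be used in any statistical analyses".

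Protocol 8.2 puts all analyses on the mITT, which is defined on any IMP and so includes placebo. Protocol 8.3.3.2 says all PD data will be summarised, 6.7.6.2 says PD change from baseline will be derived, and 6.7.7 collects immunogenicity samples from all subjects.

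**The concern.** PD is part of the primary objective, and ADA/nAb is a secondary endpoint. The ADA/nAb table cannot be produced as specified: the programmer must either deliver a placebo column with no subjects or change the population without a written basis. The same choice of population would also remove from that table any emapalumab subject excluded for a deviation affecting PK/PD evaluation, although such a subject has been exposed and is relevant to immunogenicity.

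For PD, the SAP narrows what the protocol promises and gives no reason. The protocol itself (4.1.2.3) describes the rise in total IFNγ in NI-0501-03 by contrast with placebo. The documents give no placebo values for CXCL9 or sIL2R.

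**Working it through.** **Arm sizes.** SAP 4.1 and 4.3 give 8 subjects randomised 3:1. 8 × 3/4 = 6 emapalumab and 8 × 1/4 = 2 placebo, which reproduces the stated 6 and 2.

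**Applying the definitions.** Assume all 8 are dosed as randomised, have a blood draw and have no relevant deviation.

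| Set | Emapalumab | Placebo |
|---|---|---|
| PK/PD (SAP 7.2) | 6 | 0 |
| mITT (SAP 7.1, protocol 8.2) | 6 | 2 |
| Safety (SAP 7.3) | 6 | 2 |

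Misdosing does not change the zero. Anyone in the PK/PD set has received emapalumab, and grouping is by treatment received.

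**ADA/nAb table (15.4.1).** The placebo percentage is 0/0, which is undefined. On the Safety Analysis population it would be x/2.

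For emapalumab, suppose for illustration that one of 6 is ADA-positive: 1/6 = 16.7%. If one ADA-negative subject is excluded for a PK/PD-affecting deviation, the table shows 1/5 = 20.0%. If the excluded subject is the positive one, it shows 0/5. The documents do not say how likely such an exclusion is. SAP 7.2 does not list the qualifying deviations. Protocol 9.4 lists deviations to be notified to the CRO, including an incorrect dose, but does not say which of them affect PK/PD.

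**Demographics (10.1).** The PK/PD version has placebo N = 0. The Safety version has placebo N = 2, so no information is lost.

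**PD outputs (14.2.1 to 14.2.3).** Placebo is in 0 of 3. SAP Table 1 schedules PD at pre-infusion and 1, 2, 4, 8 and 10 h (6), Days 2, 3, 5 and 8 (4), and Weeks 2, 4, 6 and 14 (4): 6 + 4 + 4 = 14 time points. Two placebo subjects × 14 = 28 scheduled PD sampling occasions with no planned table or figure.

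**PD change from baseline.** Protocol 6.7.6.2 plans it for total IFNγ, CXCL9 and sIL2R. SAP 14.2 does not, although SAP 15.3.1 and 15.5.1 plan it for laboratory data and vital signs. This omission is not caused by the definition in 7.2.

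**What two placebo subjects can show.** The 95% half-width of a mean with n = 2 is t(0.975, 1 df)/√2 = 12.706/1.414 = 8.98 SD. For 0/2 ADA-positive, the exact two-sided 95% upper limit is 1 − √0.025 = 84.2%.

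**The case against.** The strongest defence is that little is lost. SAP 16 plans listings of ADAs and nAbs and of PD biomarkers, and SAP 8 says all endpoints are presented individually in listings. With two placebo subjects, and ADA sampled only before infusion and at completion, a listing can carry everything a placebo column would. Protocol 8.3.4.3 does not ask for ADA by group. The primary objective concerns emapalumab after an emapalumab dose, so emapalumab-only PD summaries fit it, and each subject's pre-dose value provides a within-subject reference.

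Most of this stands as a limit on the consequences. It does not make 15.4.1 executable, reconcile it with SAP 7.3, or explain the departure from protocol 8.2 and 8.3.3.2. The within-subject argument also makes the missing change from baseline harder to defend.

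A reader might think that SAP 8.3.2 settles the empty column: "Percentages will be suppressed when the count is zero, however the category will still be displayed". That rule covers a zero count, not a zero denominator.

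A reader might also infer that 14.2.1 to 14.2.3 have empty placebo columns. They do not, because they never request a placebo group. Only 15.4.1 and the PK/PD version of 10.1 do. SAP 9.3 is not contradictory either, since placebo subjects can simply be counted as unqualified for the PK/PD population.

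**Conclusion.** The point holds as three separate items. First, 15.4.1 is wrong as written: its placebo denominator is 0 instead of 2, it conflicts with SAP 7.3, and it can drop an exposed emapalumab subject. The matching fault in 10.1 is cosmetic. Second, the 2 placebo subjects are in none of the three planned PD outputs, an unexplained departure from the protocol, and the SAP disagrees with itself on whether the mITT is used. Third, the PD change from baseline is missing from SAP 14.2.

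The weight is minor to should-fix. No hypothesis test, alpha or power depends on any of this. The counts assume that all 8 subjects are dosed as randomised; the 1/5 and 0/5 cases are illustrations, not forecasts.

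The documents do not support saying that the placebo data are lost, because neither listing is stated to be restricted to emapalumab. Nor do the earlier ADA rate in healthy subjects (1 of 14, protocol 4.4) or the IFNγ contrast in NI-0501-03 measure the size of this fault. The first ignores whether anyone is excluded, and the second describes a drug effect in another study.

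**What to change.** - **15.4.1:** use the Safety Analysis population.
- **7.2 and 14.2.1 to 14.2.3:** define the set on an infusion of IMP instead of emapalumab, and keep the exclusion for PK/PD-affecting deviations. Add placebo as a second group in the PD outputs, shown as individual values and not as mean ± SD. The PK outputs stay emapalumab-only through their own group lines, 10.1 becomes consistent, and 9.3 needs no change.
- **14.2:** add a PD change-from-baseline summary.
- **7 and 7.1:** make the two agree on whether the mITT is used, and record the departures from protocol 8.2 with reasons.

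Moving PD to the mITT would also bring placebo in. It would, however, remove the deviation exclusion from a primary endpoint and could leave PK and PD resting on different emapalumab subjects, so the edit to 7.2 is preferable.

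The cost is SAP wording and a little programming, with no new samples or visits. SAP 5.2 allows revision before database lock. The gain is modest, because two placebo subjects are only a weak descriptive reference.
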